11.1 ADVERSE EVENTS

Adverse events will be coded by system organ class and preferred term using the *Medical Dictionary for Regulatory Activities* (MedDRA), version 22.0 or newer.

An AE will be considered as a treatment-emergent adverse event (TEAE) if the AE began or worsened (increased in severity or became serious) on or after the date of the first double-blinded dose of the lead-in study treatment. An AE that occurs more than 30 days after the last dose of study treatment in this study or safety follow-up visit (Visit 12) whichever comes later will not be counted as a TEAE. Per case report form instructions, a new AE record will be created for any AE that worsens; therefore, TEAEs can be identified as those AEs with recorded onset date on or after the date of the first dose of lead-in study treatment and within 30 days after the last dose of open-label study treatment or Visit 12 whichever comes later. An AE will be considered as a treatment-emergent SAE (TESAE) if it is a TEAE that also meets SAE criteria. TEAEs that started after the date of last dose of open-label study treatment will be considered as newly emergent. Only TEAEs that started on or after the date of first dose of open-label study treatment will be summarized for this study.

Overall summary of AEs will be provided on a per-participant basis for categories of TEAEs, treatment-related TEAEs, deaths, TESAEs, and TEAEs leading to study intervention discontinuation.

The number and percentage of participants reporting TEAEs will be tabulated by system organ class and preferred term, and further categorized by severity and causal relationship to the study treatment. If more than 1 AE is coded to the same preferred term for the same participants, the participant will be counted only once for that preferred term using the greatest severity and strictest causality for the summarization by severity and causal relationship.

The number and percentage of participants reporting newly emergent TEAEs will be tabulated by system organ class and preferred term.

The number and percentage of participants who have TEAEs leading to premature discontinuation of the study intervention will be summarized by system organ class, preferred term.

The incidence of common ($\geq 2\%$ [after rounding] of participants) TEAEs will be summarized by preferred term.

The number and percentage of participants who have TESAE will be tabulated by system organ class and preferred term.

In addition, separate tabular displays will be presented for participants who died, participants with SAEs, and participants with TEAEs leading to study intervention discontinuation.

All AE reports in this study will be summarized or listed.

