### **4.2 Inclusion Criteria**

1. Written informed consent and participant privacy information (eg, written authorization for use and release of health and research study information) obtained from the participant prior to initiation of any study-specific procedures.
2. Participants must be using a medically acceptable and effective method of birth control during the course of the entire study, as defined in [Section 4.4.3](#).
3. Eligible participants who completed the double-blind treatment period (Visit 7) and the follow-up period (Visit 8), if applicable, depending on the timing of study initiation, of Study 3101-301-002 without significant protocol deviations (eg, noncompliance to protocol-required procedures) and who did not experience an AE that, in the investigator's opinion, may indicate an unacceptable safety risk.

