7.0 PARTICIPANT DISPOSITION

Screen-failures and the associated reasons for failure will be tabulated for all screened participants.

The number of participants in the 2 study populations (Screened, Safety) will be summarized overall.

The number of participants in the safety population will be summarized by lead-in study treatments (placebo, Atogepant 10 mg, Atogepant 30 mg, Atogepant 60 mg) and enrollment category (3101-301-002 Visit 7 Completer, 3101-301-002 Visit 8 Completer, 3101-301-002 Study Completer) and overall.

The number and percentage of participants who enter the open-label treatment period, complete the open-label treatment period and of participants who prematurely discontinue during the same period will be presented for the Safety Population. The reasons for premature discontinuation from the open-label treatment period will be summarized (number and percentage). Similar disposition information to the treatment period will be presented for the safety follow-up period. All participants who prematurely discontinue during the open-label treatment period or the safety follow-up period will be listed by discontinuation reason.

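### The open-label onset cut in SAP 11.1 drops from the discontinuation tables a TEAE that began before the first open-label dose, did not worsen after it, and led to stopping atogepant

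*SAP*

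**What the plan says.** SAP 11.1 treats an AE as emergent when it starts or gets worse "on or after the date of the first double-blinded dose of the lead-in study treatment". The SAP's own words for the qualifying change are that the event "began or worsened (increased in severity or became serious"). The window closes 30 days after the last open-label dose or at Visit 12, whichever is later. An event that began during the lead-in study is therefore a TEAE by definition.

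The same section then narrows what is reported: "Only TEAEs that started on or after the date of first dose of open-label study treatment will be summarized for this study". Worsening is handled by a data rule: "Per case report form instructions, a new AE record will be created for any AE that worsens".

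TEAEs leading to discontinuation of study intervention are one category of the overall AE summary. There is also a dedicated table, counting those "who have TEAEs leading to premature discontinuation of the study intervention will be summarized by system organ class, preferred term". Neither is exempted from the onset restriction. The end of SAP 11.1 adds a separate display of participants with such TEAEs, and promises that every AE report will be either summarized or listed.

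SAP 7.0 reports discontinuation without any reference to AE onset: "The reasons for premature discontinuation from the open-label treatment period will be summarized (number and percentage"). AE is one of the reasons in Protocol 8.8. On entry, criterion 3 of Protocol 4.2 admits "Eligible participants who completed the double-blind treatment period (Visit 7"), unless a lead-in AE led the investigator to judge continued participation unsafe.

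**The concern.** An onset cut suits incidence: it stops events already reported in the lead-in study from being counted again as new. It suits discontinuation less well, because the event of interest there is the stopping of open-label drug, which can happen only in this study. A participant may roll over with a tolerable ongoing event and later stop atogepant because of it, with no change of grade. That is a tolerability failure on open-label treatment, yet the onset date removes it from the table meant to show such failures.

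Safety and tolerability are the study's only objective (Protocol 2.1, SAP 5.0), and stopping for an adverse event is among the most direct measures of tolerability. The restriction can remove participants from this count but can never add any. The same report may also show an AE count in disposition that differs from the count in the AE tables, with no planned explanation.

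**Working it through.** The plan states no figure to reproduce. It reports no sample size calculation (SAP 16.0) and no expected discontinuation rate. The check applies the counting rule to cases and then sizes one omission.

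**Inputs**
- TEAE window: onset from the first lead-in dose to the later of 30 days after the last open-label dose and Visit 12 (SAP 11.1).
- Inclusion in summaries: onset on or after the first open-label dose (SAP 11.1).
- New record: created when an event worsens, meaning a higher severity or becoming serious (SAP 11.1). Leading to discontinuation is not named as a trigger.
- Planned enrolment: about 750 (Protocol 7.4, SAP 16.0).

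**Step 1: apply the rule**

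| Case, each ending in a stop of open-label atogepant | TEAE? | In the discontinuation summaries? |
|---|---|---|
| A. Lead-in onset, unchanged afterwards | Yes | No |
| B. Lead-in onset, worsens on open-label drug, stop recorded on the new record | Yes | Yes |
| C. Open-label onset | Yes | Yes |
| D. Onset on the date of the first open-label dose | Yes | Yes |
| E. Lead-in onset, worsened only before the first open-label dose | Yes | No |

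The gap is confined to cases A and E. An event that begins between the end of lead-in treatment and a delayed Visit 1 (a gap that Protocol 3.1 allows) and then stays unchanged is treated like A.

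**Step 2: does another table count the stop?** It is not a discontinuation of lead-in treatment, because the participant completed the double-blind period in order to enter. Disposition counts the participant under AE if that is the recorded reason, but does not name the event. Listings should show it. The separate display in SAP 11.1 may show it: it refers to TEAEs, which by definition include lead-in onset, but the SAP does not say whether the onset restriction governs a display as well as a summary.

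**Step 3: size**

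Reported percentage = (true number − omitted number) / 750. Each omission changes it by 1/750 = 0.13 percentage points.

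The true and omitted numbers below are assumptions, chosen only to show scale.

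| Assumed true AE discontinuations | 1 omitted | 3 omitted | 5 omitted | 8 omitted |
|---|---|---|---|---|
| 15 (2.0%) | 14/750 = 1.87% | 12/750 = 1.60% | 10/750 = 1.33% | 7/750 = 0.93% |
| 30 (4.0%) | 29/750 = 3.87% | 27/750 = 3.60% | 25/750 = 3.33% | 22/750 = 2.93% |
| 45 (6.0%) | 44/750 = 5.87% | 42/750 = 5.60% | 40/750 = 5.33% | 37/750 = 4.93% |

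**The case against.** The strongest reply is that the restriction looks deliberate and that little escapes it. The SAP's summary of changes records a sentence added to 11.1 to handle AEs captured at visits shared by the two studies. Many events that become intolerable will also rise in grade, because Protocol 9.1.3 grades intensity by interference with daily activities. Those events get a new record and are counted. Entry criteria remove participants whose lead-in event worried the investigator, and completing double-blind treatment selects people who tolerated it. All of this stands, and it limits the gap to non-worsening events. It does not close the gap, and the reason for the cut concerns incidence rather than stopping open-label drug.

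A second reply concerns placebo. SAP 7.0 lists placebo among the lead-in treatments. An event that began on placebo is not an atogepant-onset event, and there is a case for keeping it out of atogepant tables. This also stands. It calls for showing such events separately rather than omitting them without comment.

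Three stronger readings are tempting, and the documents do not support them:
- A reader might infer that every lead-in-onset event leading to a stop is lost. Case B shows otherwise.
- A reader might infer a large bias. If 10% to 30% of 750 carried over an event and 1% to 5% of those stopped for it, the loss would be 750 × 0.10 × 0.01 = 0.75 to 750 × 0.30 × 0.05 = 11.25 participants. Nothing in the documents supports either pair of rates.
- A reader might infer that the AE tables and disposition must agree once the cut is lifted. They measure different things. SAP 11.1 counts discontinuation of study intervention. Protocol 8.8 assigns one reason for leaving the study, and Protocol 9.5 allows for rechallenge after a stop.

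**Conclusion.** The concern holds in a limited form. As SAP 11.1 is written, a TEAE with onset before the first open-label dose and no later worsening, which leads to stopping open-label atogepant, is absent from the overall-summary discontinuation row and from the discontinuation table by system organ class and preferred term. The effect can only be an understatement, of 0.13 percentage points per omitted participant at 750. The number omitted cannot be estimated from the documents and may be very small.

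The conclusion rests on two assumptions. One is that only worsening creates a new AE record: the SAP says that worsening does so, but the case report form instructions that it relies on are not among the documents. The other is that the sentence on what is summarized covers the discontinuation category, which is the plain reading since no exception is made. The information is not lost from the report as a whole. It is missing from the tables where a reader would look for it, and the scope of the separate display is unclear.

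**What to change.** Leave the onset cut in place for the incidence tables. Add to SAP 11.1 that the discontinuation row of the overall summary, the discontinuation table by system organ class and preferred term, and the separate display count TEAEs whose recorded action is withdrawal of open-label atogepant on or after the first open-label dose, whatever their onset within the TEAE window. Keeping to the TEAE window leaves out events that predate lead-in treatment.

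Present onset on or after the first open-label dose and onset before it as separate rows, with the earlier-onset row split by lead-in treatment (placebo or atogepant). Add a footnote explaining any difference from the AE reason in the SAP 7.0 disposition table, without requiring the two counts to be equal.

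The cost is a sentence or two and a few table rows. No new data are needed, because Protocol 6.5.1 already requires the action taken to be documented for every AE. The documents do not say which study's AE file holds a carried-over event, so the derivation should search both. The downside is that the reported discontinuation rate may be slightly higher and may include some events that began on lead-in placebo; the split rows make that visible. No clinical rule changes.

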11.2 CLINICAL LABORATORY PARAMETERS

Descriptive statistics for clinical laboratory values (in SI units) at baseline, postbaseline, and changes from baseline values at each postbaseline timepoint will be presented for the following laboratory parameters.

In addition, descriptive statistics for values and changes from the baseline values in conventional units at each assessment time point will be presented for selected clinical laboratory parameters listed in [Appendix I](#). A description of reporting the lab values in conventional units in patient narratives (along with the standard reporting in SI units) is presented at the end of [Appendix I](#).

Hematology: Hemoglobin, hematocrit, red blood cell count, red blood cell indices (mean corpuscular volume, mean corpuscular hemoglobin, mean corpuscular hemoglobin concentration), white blood cell count, including differential (neutrophils, lymphocytes, monocytes, eosinophils, and basophils), platelet count

Chemistry: Sodium, potassium, chloride, bicarbonate, glucose, blood urea nitrogen, creatinine, total bilirubin, alkaline phosphatase, aspartate aminotransferase, alanine aminotransferase, lactate dehydrogenase, creatine kinase, total protein, albumin, calcium, phosphorus, uric acid, total cholesterol, estimated glomerular filtration rate

Urinalysis: Specific gravity, pH

Clinical laboratory test values will be considered potentially clinically significant (PCS) if they meet either the lower-limit or higher-limit PCS criteria listed in [Table 11-1](#). The number and percentage of participants who have PCS postbaseline clinical laboratory values will be tabulated. The percentages will be calculated relative to the number of participants with available non-PCS baseline values and at least 1 postbaseline assessment. The numerator will be the total number of participants with available non-PCS baseline values and at least 1 PCS postbaseline value during the study. A supportive tabular display of participants with PCS postbaseline values will be provided, including the participant identification (PID) number, baseline and all postbaseline (including non-PCS) values.

In addition, a tabular display showing all AEs that occurred in participants who had PCS postbaseline clinical laboratory values will be provided.

Potential Hy's Law criteria within a 24-hour window is defined by a postbaseline elevation of alanine aminotransferase (ALT) or aspartate aminotransferase (AST) $\geq 3 \times$ ULN, along with total bilirubin (TBL) $\geq 2 \times$ ULN and a non-elevated alkaline phosphatase (ALP) $< 2 \times$ ULN, all based on blood draws collected within a 24-hour period. Participants who meet the potential Hy's Law criteria from the first dose of study treatment to the end of study will be summarized. Supportive tabular displays will also be provided.

Table 11-1 Criteria for Potentially Clinically Significant Laboratory Values

Category	Parameter	SI Unit	PCS Criteria	
			PCS Low	PCS High
Chemistry	Albumin	g/L	< 0.8 × LLN	> 1.2 × ULN
	Alanine aminotransferase	U/L	—	≥ 3.0 × ULN
	Alkaline phosphatase	U/L	—	≥ 3.0 × ULN
	Aspartate aminotransferase	U/L	—	≥ 3.0 × ULN
	Bicarbonate	mmol/L	< 0.9 × LLN	> 1.1 × ULN
	Bilirubin, total	μmol/L	—	≥ 1.5 × ULN
	Blood urea nitrogen	mmol/L	—	> 1.5 × ULN
	Calcium	mmol/L	< 0.9 × LLN	> 1.1 × ULN
	Chloride	mmol/L	< 0.9 × LLN	> 1.1 × ULN
	Cholesterol, total	mmol/L	—	> 1.6 × ULN
	Creatinine	μmol/L	—	> 1.5 × ULN
	Creatine kinase	U/L	—	> 2.0 × ULN
	Estimated glomerular filtration rate	mL/min/1.73m ²	<60 mL/min/1.73 m ²	—
	Glucose, nonfasting	mmol/L	< 0.8 × LLN	> 2.0 × ULN
	Lactate dehydrogenase (LDH)	U/L	—	> 3.0 × ULN
	Phosphorus	mmol/L	< 0.9 × LLN	> 1.1 × ULN
	Potassium	mmol/L	< 0.9 × LLN	> 1.1 × ULN
	Protein, total	g/L	< 0.9 × LLN	> 1.1 × ULN
	Sodium	mmol/L	< 0.9 × LLN	> 1.1 × ULN
	Uric acid	μmol/L	—	> 1.2 × ULN
Hematology	Basophils, absolute cell count	10 ⁹ /L	—	> 2.0 × ULN
	Eosinophils, absolute cell count	10 ⁹ /L	—	> 2.0 × ULN
	Hematocrit	Ratio	< 0.9 × LLN	> 1.1 × ULN
	Hemoglobin	g/L	< 0.9 × LLN	> 1.1 × ULN
	Lymphocytes, absolute cell count	10 ⁹ /L	< 0.7 × LLN	> 1.3 × ULN
	Monocytes, absolute cell count	10 ⁹ /L	< 0.5 × LLN	> 2.0 × ULN
	Neutrophils, absolute cell count	10 ⁹ /L	< 0.7 × LLN	> 1.3 × ULN
	Platelet count	10 ⁹ /L	< 0.5 × LLN	> 1.5 × ULN
	Red blood cell count	10 ¹² /L	< 0.9 × LLN	> 1.1 × ULN
	White blood cell count	10 ⁹ /L	< 0.9 × LLN	> 1.5 × ULN
Urinalysis	pH	pH	< 0.9 × LLN	> 1.1 × ULN
	Glucose		—	At least 1+
	Protein		—	At least 1+
	Specific gravity	—	—	> 1.1 × ULN

LLN = lower limit of normal value; ULN = upper limit of normal value; normal value provided by laboratory.

SI = Le Système International d'Unités (International System of Units).

The number and percentage of participants meeting each of the following criteria for postbaseline hepatic laboratory abnormalities listed in Table 11-2 will be summarized. The percentages will be calculated relative to the number of participants with at least 1 available postbaseline assessment. The numerator will be the total number of participants having at least 1 postbaseline value that meets the specific category during the study. A supportive listing will also be provided.

Table 11-2 Criteria for Hepatic Laboratory Abnormalities

Laboratory Parameter	Categories
ALT	$\geq 1 \times \text{ULN}$
	$\geq 1.5 \times \text{ULN}$
	$\geq 2 \times \text{ULN}$
	$\geq 3 \times \text{ULN}$
	$\geq 5 \times \text{ULN}$
	$\geq 10 \times \text{ULN}$
	$\geq 20 \times \text{ULN}$
AST	$\geq 1 \times \text{ULN}$
	$\geq 1.5 \times \text{ULN}$
	$\geq 2 \times \text{ULN}$
	$\geq 3 \times \text{ULN}$
	$\geq 5 \times \text{ULN}$
	$\geq 10 \times \text{ULN}$
	$\geq 20 \times \text{ULN}$
ALT or AST	$\geq 1 \times \text{ULN}$
	$\geq 1.5 \times \text{ULN}$
	$\geq 2 \times \text{ULN}$
	$\geq 3 \times \text{ULN}$
	$\geq 5 \times \text{ULN}$
	$\geq 10 \times \text{ULN}$
	$\geq 20 \times \text{ULN}$
Bilirubin Total	$\geq 1 \times \text{ULN}$
	$\geq 1.5 \times \text{ULN}$
	$\geq 2 \times \text{ULN}$
	$\geq 3 \times \text{ULN}$
	$\geq 5 \times \text{ULN}$
	$\geq 10 \times \text{ULN}$
	$\geq 20 \times \text{ULN}$
Alkaline Phosphatase	$\geq 1 \times \text{ULN}$
	$\geq 1.5 \times \text{ULN}$
	$\geq 2 \times \text{ULN}$
	$\geq 3 \times \text{ULN}$
	$\geq 5 \times \text{ULN}$
	$\geq 10 \times \text{ULN}$
	$\geq 20 \times \text{ULN}$

Laboratory Parameter	Categories
Concurrent Elevations ¹	ALT or AST $\geq 3 \times$ ULN and Bilirubin Total $\geq 1.5 \times$ ULN ALT or AST $\geq 3 \times$ ULN and Bilirubin Total $\geq 2 \times$ ULN
Potential Hy's Law within 24-hour window ¹	Postbaseline assessment of the following laboratory parameters based on blood draws collected within a 24-hour period: 
• ALT or AST $\geq 3 \times$ ULN• TBL $\geq 2 \times$ ULN• ALP $< 2 \times$ ULN
e-DISH	Postbaseline assessment of the following laboratory parameters at any time: 
• Maximum ALT or AST $\geq 3 \times$ ULN• Maximum TBL $\geq 2 \times$ ULN

ALT = alanine aminotransferase; AST = aspartate aminotransferase; TBL = total bilirubin;
ALP = alkaline phosphatase; ULN = upper limit of normal (value provided by the laboratory).
¹ Elevations are from the same day

The number and percentage of participants with an adjudicated case (i.e., ALT $\geq 3 \times$ ULN and/or AST $\geq 3 \times$ ULN) will be summarized and by relationship of ALT or AST elevation to study medication. The percentages will be calculated relative to the number of participants with at least 1 adjudicated case. The numerator will be the number of participants with at least 1 adjudicated case in the specific category of relationship. If a participant has more than 1 adjudicated case, he or she will be counted in the most relevant category of relationship.

Participants with an adjudicated case (i.e. ALT $\geq 3 \times$ ULN or AST $\geq 3 \times$ ULN) will be listed with their ALT and AST assessments, adjudication dates, relationship of ALT or AST elevation to study medication, and confounding factor(s). Additional listings will be provided for participants who meet ALT $\geq 3 \times$ ULN or AST $\geq 3 \times$ ULN and/or potential Hy's law and have one of the following categories: at least 1 abnormal liver biochemistry risk factor, at least 1 liver disease sign and symptom, at least 1 liver diagnostic test performed, consultation with a specialist for liver evaluation, liver lab tests performed, and drug screen performed, respectively.

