**Table 6–2. Clinical Laboratory Parameters**

Category	Parameter
Chemistry	Sodium, potassium, chloride, bicarbonate, glucose, blood urea nitrogen, creatinine, total bilirubin, alkaline phosphatase, aspartate aminotransferase, alanine aminotransferase, lactate dehydrogenase, creatine kinase, total protein, albumin, calcium, phosphorus, uric acid, total cholesterol. The estimated glomerular filtration rate will be calculated by the central laboratory
Hematology	Hemoglobin, hematocrit, red blood cell count, red blood cell indices (mean corpuscular volume, mean corpuscular hemoglobin, mean corpuscular hemoglobin concentration), white blood cell count, including differential (neutrophils, lymphocytes, monocytes, eosinophils, and basophils), platelet count
Urinalysis	Urine dipstick for specific gravity, pH, protein, glucose, ketones, bilirubin, and blood; microscopic examination including red blood cells/high-power field, white blood cells/high-power field, and casts/low-power field
Coagulation	INR
Serology	At Visit 1 only: anti-hepatitis A IgM antibody, hepatitis B surface antigen, anti-hepatitis C antibody, anti-hepatitis E IgM antibody
Urine Drug Screen	Screening for drugs of abuse (eg, marijuana, cocaine, phencyclidine, amphetamines, benzodiazepines, barbiturates, opiates) will be conducted using a urine drug screen at Visit 1. Those with a positive result on the Visit 1 urine drug screen for recreational (including marijuana regardless of legality) or illicit drugs or non-disclosed concomitant medications are not allowed to be repeated. For all other positive results, the urine drug screen may be repeated with permission from Allergan; a negative result or an explanation of a positive result due to concomitant medication use (eg, opioids prescribed for migraine pain) will be required for study participation.

IgM = immunoglobulin M; INR = International Normalized Ratio

A central laboratory will be used to evaluate all urine and blood samples, which will be collected, processed, and stored according to the instructions provided by the laboratory.

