18.9 CHARACTER VALUES OF CLINICAL LABORATORY PARAMETERS

If the reported value of a clinical laboratory parameter cannot be used in a statistical summary table because, for example, a character string is reported for a parameter of the numeric type, a coded value must be appropriately determined for use in the statistical analyses. The actual values, however, as reported in the database will be presented in the data listings.

Table 18.9–1 shows examples of how some possible laboratory results should be coded for the analysis.

Table 18.9–1 Examples of Coding Special Character Values for Clinical Laboratory Parameters

Laboratory Test, SI Unit	Possible Laboratory Results	Coded Value for Analysis
CHEMISTRY		
ALT, U/L	< 5	5
AST, U/L	< 5	5
Bilirubin, total, μ mol/L	< 2	2
URINALYSIS		
Glucose, mmol/L	= OR $> 55, \geq 55, > 0$	Positive
	≤ 0 , negative	Negative
pH	$> 8.0, \geq 8.0$	8.0
	≥ 8.5	8.5
Protein	= OR $> 3.0, \geq 3.0, > 0$	Positive
	≤ 0	Negative

ALT = alanine aminotransferase; AST = aspartate aminotransferase; SI = *Le Système International d'Unités* (International System of Units).

19.0

CHANGES TO ANALYSES SPECIFIED IN PROTOCOL

None

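### The only PCS criterion for urine specific gravity in SAP Table 11-1 (above 1.1 × ULN) cannot be met, so its row is a structural zero

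*SAP*

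**What the plan says.** SAP Section 11.2 classes a laboratory value as PCS "if they meet either the lower-limit or higher-limit PCS criteria listed in" Table 11-1. For specific gravity the table reads "Specific gravity — — > 1.1 × ULN". The two dashes stand for no unit and no PCS low limit, so the high limit is the only criterion. The table's footnote gives the source of the limits as "normal value provided by laboratory"; neither document states a ULN for specific gravity.

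Protocol Table 6-2 describes the method: "Urine dipstick for specific gravity, pH, protein, glucose, ketones, bilirubin, and blood".

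The PCS table counts participants who have a non-PCS baseline and "at least 1 PCS postbaseline value during the study". The denominator is participants with a non-PCS baseline and a postbaseline assessment. Section 11.2 adds two displays: the values of participants with a PCS result, and all adverse events in those participants.

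In the same urinalysis block, glucose and protein have a criterion on the dipstick's own scale (a grade of 1+ or more). Urine pH has two limits, "< 0.9 × LLN > 1.1 × ULN". Specific gravity and pH also receive descriptive statistics of values and changes from baseline at each postbaseline timepoint.

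**The concern.** A multiplier on the ULN suits a quantity whose natural zero is zero, such as a serum concentration. Specific gravity starts at 1.000, and everything informative about a urine sample lies in the second and third decimals. Ten per cent above the ULN is then a very large step: it adds at least 0.100 to a quantity whose whole working range is assumed here to span 0.030 to 0.060 above water.

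If no sample can exceed the limit, the row will print 0% whatever the data show. A reader of the clinical study report cannot tell that figure from an observed absence of abnormal values. Safety is the study's only objective, and Section 11.2 plans no laboratory shift table, so the PCS table is the only planned categorical summary of specific gravity.

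**Working it through.** The plan states no figure to reproduce here. The check is direct arithmetic on the stated criterion.

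**Inputs**
- Multiplier 1.1 and no low limit: SAP Table 11-1.
- ULN for specific gravity: not in the documents. Assumed 1.020 to 1.050, with 1.000 (water) as the floor.
- Top dipstick reading: not in the documents. Assumed 1.030 to 1.060.

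**Step 1: the limit.** Limit = 1.1 × ULN.

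| ULN | Limit | (Limit − 1) / (ULN − 1) |
|---|---|---|
| 1.000 | 1.100 | not defined |
| 1.020 | 1.122 | 6.1 |
| 1.030 | 1.133 | 4.4 |
| 1.040 | 1.144 | 3.6 |
| 1.050 | 1.155 | 3.1 |

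At a ULN of 1.030, for example, a sample would have to exceed water by 0.133, against 0.030 for the ULN itself.

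**Step 2: the ULN that would be needed.** A top reading m is flagged only if 1.1 × ULN < m, that is, ULN < m / 1.1.
- m = 1.030: ULN below 1.030 / 1.1 = 0.936
- m = 1.040: ULN below 0.945
- m = 1.050: ULN below 0.955
- m = 1.060: ULN below 0.964

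Each of these is less than water, so none can be a urine ULN. The result does not depend on which value in the assumed ranges is right.

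**Step 3: the effect on the displays.** With no attainable high limit and no low limit, no baseline value is PCS and no postbaseline value is PCS. No one is removed from the denominator for a PCS baseline, so it is everyone with a baseline and a postbaseline value, out of about 750 planned. The numerator is 0. Both supporting displays are empty for this parameter.

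**Step 4: does urine pH share the fault?** pH limits are 1.1 × ULN (high) and 0.9 × LLN (low), with the laboratory's limits again unknown.
- Assumed ULN 7.0, 7.5, 8.0, 8.5, 9.0 gives high limits 7.70, 8.25, 8.80, 9.35, 9.90.
- SAP Table 18.9-1 includes a result coded as 8.5. It is flagged whenever ULN < 8.5 / 1.1 = 7.73, so at 7.0 and 7.5 but not at 8.0 or above. A reported 9.0 would be flagged at a ULN of 8.0 (9.0 > 8.80).
- Assumed LLN 4.5, 5.0, 5.5, 6.0 gives low limits 4.05, 4.50, 4.95, 5.40. A reading of 4.5 is flagged at an LLN of 5.5, and a reading of 5.0 at an LLN of 6.0.

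For pH the answer depends on the laboratory's range; for specific gravity it does not.

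**The case against.** The best reply is that very little rests on this row. Specific gravity is still summarised at each timepoint, and SAP Section 18.3 puts all assessments in the data listings. Protocol Section 6.5.3 has the investigator judge the clinical significance of values outside the central laboratory's range, and Protocol Section 9.1.1 allows an abnormal laboratory finding to be an adverse event. Creatinine, blood urea nitrogen, estimated glomerular filtration rate, urine protein and urine glucose each have their own PCS criterion. No conclusion in this single-arm descriptive study turns on specific gravity. All of that stands, and it limits the size of the point. It does not make the criterion workable.

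A second reply is that neither the ULN nor the attainable range of urine is in the documents. That is so, but the conclusion holds at every assumed value, including the floor of 1.000.

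A reader might go further and infer that urine pH has the same fault, because at a ULN of 8.0 the high limit is 8.8 and the highest pH in Table 18.9-1 is 8.5. The documents do not support that. The ULN of 8.0 is an assumption. Table 18.9-1 gives only "examples of how some possible laboratory results should be coded for the analysis", so 8.5 is not shown to be the highest reportable pH. And pH has a low limit that can trigger PCS by itself.

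**Conclusion.** The specific gravity criterion is wrong as written: a stated threshold that cannot do its job. The PCS count for specific gravity during the study is 0 by construction. This is one per-participant count over the whole study; the PCS table is not broken down by visit.

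The conclusion rests on two things outside the documents: that a urine ULN is at least 1.000, which follows from what specific gravity measures, and that the top dipstick reading lies somewhere from 1.030 to 1.060. Any top reading up to 1.100 would give the same answer.

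The consequence is minor. One row of a descriptive safety table carries no information and could be misread as reassurance. It would be too much to say that specific gravity goes unexamined, or that the pH row is also empty. For pH the documents leave the matter open until the laboratory's limits are known.

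**What to change.** In SAP Table 11-1, do one of the following for specific gravity:
- delete the row from the PCS table and keep the descriptive statistics and listings; or
- replace the multiplier with an absolute limit on the dipstick's own scale that lies within its reportable range, as the same block already does for glucose and protein, and as the table does for estimated glomerular filtration rate (below 60).

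Simply using values above the ULN is not a good substitute. Every other row based on the ULN or LLN applies a margin, so this one would come to mean outside the reference range. With up to 11 postbaseline visits (Visits 2 to 12), a single such dipstick reading would bring all of a participant's adverse events into the PCS display. The documents give no basis for saying how many participants that would be.

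For urine pH, check that 0.9 × LLN and 1.1 × ULN can be reached given the central laboratory's reference range and reportable values. Change the row only if they cannot.

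The cost is one table cell and one query to the laboratory, with no new data.
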